#### **4.1.3 Open-label Extension**

After completion of the double-blind treatment period, all participants will have the option of entering an OLE period, during which they will receive benralizumab 30 mg Q4W for at least 1 year. Assessments will be conducted according to the SoA ([Table 2](#)). During the OLE

participants can receive corticosteroids (topical and/or oral) for BP relapse at the Investigator's discretion, with the goal of tapering off the steroids to benralizumab monotherapy as soon as clinically indicated. If in the opinion of the Investigator, a participant requires the addition of immunosuppressants, the participant will discontinue benralizumab and will withdraw from the OLE. Participants will be asked to complete the follow-up visit assessment 12 weeks after their last dose according to the SoA ([Table 2](#)). Participants may additionally be asked to allow future contact to provide follow-up clinical details regarding their health and information on disease state.

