### **Intervention Groups and Duration:**

The study consists of a screening period, a randomized double-blind treatment period, and an open-label extension (OLE).

Following screening, eligible participants will be randomized 1:1 to receive either benralizumab or placebo every 4 weeks (Q4W) by SC injection during the initial 36-week, double-blind phase of the study. After randomization, participants will receive a loading dose of 60 mg benralizumab or placebo, administered as 2 SC injections. After 4 weeks, participants will receive 30 mg benralizumab or placebo Q4W until the end of the double-blind treatment period at 36 weeks. Participants will also receive OCS at 0.5 mg/kg/day (or higher if required) in addition to investigational product (IP) until BP disease control is achieved. The OCS dose can be increased, if necessary, to achieve disease control. The consolidation phase begins when disease control is achieved and continues until the time at which no new lesions or pruritic symptoms have developed for a minimum of 2 weeks and the majority of established lesions have healed (end of consolidation phase). At this point, participants will begin protocolled OCS tapering, with the aim to taper off OCS completely within 3 to 4 months (ie, 4 to 5 months from randomization).

After completion of the double-blind treatment period, all participants will have the option of entering an OLE period for at least 1 year, during which they will receive benralizumab 30 mg Q4W until study closure. During the OLE participants can receive OCS to address the BP relapse at the Investigator's discretion, with the goal of tapering off the steroids to benralizumab monotherapy as soon as clinically indicated.

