The primary endpoint chosen is to assess the effect of benralizumab on sustained disease remission. This endpoint was chosen based on outcome measures recommended by the consensus statement ([Murrell et al 2012](#)) and feedback from a panel of clinical experts on BP who were consulted on the feasibility of using benralizumab as a treatment for BP and on the optimal study design. While OCS are the only well-established treatment for BP and highly effective for achieving disease control, the relapse rate is high on tapering and discontinuation, and OCS are associated with significant morbidity and mortality. The overall treatment goal in participants with BP is to reduce the dose of OCS and associated side effects while maintaining disease control. The ability of participants to taper steroids and achieve complete remission off steroids (the proposed primary variable) and the proportion of participants who have relapsed after tapering steroid therapy (the first key secondary variable) are therefore clinically important outcomes in this participant population. Both are accepted endpoints for BP studies ([Murrell et al 2012](#)). The key secondary variables, proportion of participants who remain relapse-free up to Week 36, cumulative OCS exposure (mg/kg) up to Week 16 and up to Week 36, and change in BPDAI activity and pruritus scores at Week 36, will also provide an opportunity to assess benralizumab's efficacy in participants with symptomatic BP.

The OLE will provide an opportunity to assess long-term safety and tolerability, in addition to assessing efficacy of benralizumab monotherapy, and to ensure that all participants who complete the double-blind treatment period can have access to treatment with benralizumab.

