#### **4.4 End of Study Definition**

The end of study is defined as the last expected visit/contact of the last participant undergoing the study. A participant is considered to have completed the study when he/she has completed his/her last scheduled visit/telephone contact.

As participants may be offered the opportunity to participate in an OLE (Section [4.1.3](#)) of at least 1 year after completing the double-blind period of the study on IP, the end of study is planned to be when the last randomized participant completes 1 year in the OLE.

However, as AstraZeneca may choose to extend the OLE period, this decision will determine when the end of the study is declared. Notification of closure of the study will be communicated to sites at least 3 months in advance of the end of study, unless faster termination is warranted (eg, emergence of a safety concern).

After the end of the study, participants should be given standard-of-care therapy, at the discretion of their treating physician, per local practice.

See [Appendix A 6](#) for guidelines for the dissemination of study results.

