## 7 DISCONTINUATION OF STUDY INTERVENTION AND PARTICIPANT DISCONTINUATION/WITHDRAWAL

### 7.1 Discontinuation of Study Intervention

Participants discontinuing from IP are strongly encouraged to continue in the study up to the end of the double-blind treatment period (Visit 13/Week 36) as described in Section 7.1.1. The IP discontinuation (IPD) visit should be done 4 weeks ( $\pm$  7 days) after the last dose of IP. Participants who discontinue IP can continue in the study until Visit 13/Week 36.

Discontinuation from IP does NOT automatically lead to a complete withdrawal from the study.

Participants will be discontinued from IP in the following situations:

- Participant decision. The participant is at any time free to discontinue treatment, without prejudice to further treatment. The participant should always be asked about the reason(s) and presence of any AEs.
- AE that, in the opinion of the Investigator, contraindicates further dosing.
- Severe non-compliance with the CSP.
- Risk to participant as judged by the Investigator or AstraZeneca.
- Pregnancy.
- IP unblinding.
- Development of any of the following study-specific criteria for discontinuation:
  - Anaphylactic reaction to IP administration, in the opinion of the Investigator, requiring administration of epinephrine.
  - Development of helminth parasitic infestation requiring hospitalization.
  - New or active malignancy.
  - If after randomization, the result of the central laboratory HIV test is positive.

Refer to the SoA (Table 2) and Section 7.1.1 (IPD visit) for data to be collected at the time of IPD and follow-up and for any further evaluations that need to be completed.

The reason for premature discontinuation of IP should be documented in the source documentation and recorded in the eCRF.

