1.2.3 Open-label extension period

After completion of the double-blind treatment period, all participants will have the option of entering an OLE period, during which they will receive benralizumab 30 mg Q4W for at least 1 year. During the OLE period participants can receive corticosteroids (topical and/or oral) for BP relapse at the Investigator's discretion, with the goal of tapering off the steroids to benralizumab monotherapy as soon as clinically indicated.

Figure 1 Study Design

BP, bullous pemphigoid; m, months; n, number of participants randomized; OCS, oral corticosteroids; OLE, open-label extension; Q4W, every 4 weeks; SOC, standard of care.

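### The documents disagree on whether a participant who stopped IP but stayed to Week 36 may enter the open-label extension

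*Protocol*

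**What the plan says.** Four places open the OLE to everyone who completes the double-blind period:

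- Protocol 4.1.3: "After completion of the double-blind treatment period, all participants will have the option of entering an OLE period".
- The protocol synopsis (Intervention Groups and Duration), in the same terms.
- Protocol 4.2, which gives as one purpose of the OLE "to ensure that all participants who complete the double-blind treatment period can have access to treatment with benralizumab".
- SAP 1.2.3: "all participants will have the option of entering an OLE period, during which they will receive benralizumab 30 mg Q4W".

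Other places point the other way:

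- Protocol 4.4, within the end-of-study definition, describes participants possibly being offered an OLE "of at least 1 year after completing the double-blind period of the study on IP".
- Protocol 7.1: "Participants who discontinue IP can continue in the study until Visit 13/Week 36".
- Footnote c of the schedule of activities (Protocol Table 2) places end of treatment at Visit 13 for those who stop IP but stay in follow-up.
- Protocol 7.1.1 says those who permanently stop IP should receive local standard of care.
- Protocol 7.1.1.1 lists the follow-up options after stopping in the double-blind period; OLE entry is not among them.

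The stopping criteria in Protocol 7.1 include, for example, "Anaphylactic reaction to IP administration, in the opinion of the Investigator, requiring administration of epinephrine", as well as new or active malignancy, pregnancy and a positive central HIV test. Protocol 6.5.1 adds stopping IP when an immunosuppressant is needed to control relapse.

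**The concern.** The first group of passages attaches no condition about still being on IP. Section 4.4 does attach one, and the others imply one without mentioning the OLE. Two sites could therefore read the same protocol and reach opposite decisions about the same participant, including one whose IP was stopped for a safety reason.

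Two things are at stake. One is whether a stopping decision made in the double-blind period carries over into the OLE, which the text should settle rather than leave to each site. The other is what the OLE and safety summaries describe. If some discontinuers enter, the OLE analysis set holds three kinds of participant: continuous users, those starting benralizumab after placebo, and those restarting after a gap. The SAP does not separate the third group.

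**Working it through.** No figure in the plan needs reproducing for the main point, which is one of textual consistency. The arithmetic concerns only the analysis effect and the number affected.

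**1. Can someone off IP complete the double-blind period?** Yes. Protocol 7.1 says stopping IP does not automatically mean withdrawal. Protocol 4.1.2 and 7.1.1.1 ask such participants to attend all visits to Week 36. SAP 4.2.1 tabulates completing study drug and completing the double-blind period as separate categories.

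**2. One case traced through the text.** A participant has anaphylaxis needing epinephrine, IP is stopped under 7.1, and the participant attends to Week 36.
- Synopsis, 4.1.3, 4.2, SAP 1.2.3: the OLE option is open.
- 4.4: the description is not met, because the period was not completed on IP.
- Footnote c, 7.1, 7.1.1, 7.1.1.1: treatment and participation appear to end at Week 36, but OLE entry is not addressed.
- Footnote a treats non-entry as the participant's own choice and states no eligibility check.

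**3. Immunosuppressant use.** In the OLE it leads to stopping benralizumab and leaving (4.1.3, 6.5.1). In the double-blind period it leads to stopping IP and staying to Week 36 (6.5.1). A participant who still needs the drug at Week 36 is covered by the OLE rule. One who no longer needs it is not clearly covered.

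**4. OLE summaries.** SAP 2.1.5 takes anyone who starts or carries on benralizumab after the double-blind period. SAP 4.2.11 summarises overall and by randomized arm only. Benralizumab-arm restarters are therefore pooled with continuous users, and placebo-arm discontinuers with the other placebo switchers.

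**5. Adverse event window (SAP 3.5.1).** For a participant who does not enter the OLE, the on-treatment window ends no later than last dose + 12 weeks. For an OLE entrant, the double-blind on-treatment window runs to the day before the first OLE dose. With the last double-blind dose at Week w and OLE entry at Week 36:

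extra weeks = 36 − (w + 12) = 24 − w, when w is below 24; otherwise 0.

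- w = 0: 24 weeks.
- w = 8: window to about Week 20 without OLE entry and about Week 36 with it, so 16 extra weeks.
- w = 24 or later: none.

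These weeks would enter both the event counts and the person-years at risk in SAP 4.2.9.1.

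**6. Exposure (SAP 4.2.4).** Exposure is last dose date minus first dose date plus 1. For the w = 8 case, the overall figure counts all 36 − 8 = 28 weeks between the last double-blind dose and the first OLE dose. The separate double-blind and OLE figures, if each uses its own first and last dose, would not include the gap.

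**7. Number affected.** The documents give no IP discontinuation rate. As an assumption, 5% to 15% of the SAP's 100 participants gives 100 × 0.05 = 5 to 100 × 0.15 = 15. This is an upper limit, since not all would stay to Week 36.

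**The case against.** The strongest reply is that the protocol, read as a whole, already keeps discontinuers out. Section 7.1 says participants will be discontinued from IP for the listed reasons, and nothing resets those reasons at Week 36. Sections 7.1.1 and 7.1.1.1 and footnote c describe a path that ends without the OLE. The 4.4 wording sits in an end-of-study definition and says only that the OLE may be offered, so it is weaker than an eligibility criterion. Section 6.1.1 requires an evaluation for contraindications before each dose, and 6.1.2 withholds IP for any event the investigator or sponsor considers a contraindication. Since Visit 13 is the first OLE dose, those checks apply there. Section 6.1.2 also calls for a discussion with the sponsor's study physician after two or more missed doses.

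Much of this stands, and it rules out some stronger readings. A reader might infer that the protocol lets a participant stopped for anaphylaxis be re-dosed without any check; 6.1.1 and 6.1.2 do not support that. A reader might infer that every discontinuer who enters is counted as a continuous benralizumab user; SAP 4.2.11 groups by randomized arm, so this holds only for the benralizumab arm. Likewise, only those randomized to benralizumab would be receiving it again; placebo-arm discontinuers would be starting it. A reader might also infer that no OLE eligibility rule exists anywhere. None appears in the text reviewed, but the protocol appendices and the IxRS manual were not part of it.

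What the reply does not do is settle entry. None of the passages it relies on mentions the OLE entry decision for discontinuers, and a dose-day judgement is not an entry rule. Four passages still say all participants.

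**Conclusion.** The inconsistency is real, and the text reviewed does not resolve it. A participant who stops IP and stays to Week 36 qualifies for the OLE under the synopsis, 4.1.3, 4.2 and SAP 1.2.3, does not fit the description in 4.4, and by implication is finished at Week 36 under footnote c and 7.1 to 7.1.1.1.

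The effect is limited. The Week 36 primary comparison, its power and the type I error rate do not depend on it, and the OLE analyses are descriptive (SAP 4.1). The exposed parts are the OLE summaries, overall exposure, and the double-blind on-treatment adverse event time for OLE entrants whose last double-blind dose was before Week 24.

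The number affected is unknown. The 5 to 15 ceiling rests on the assumed 5% to 15% stopping rate; those stopped under a safety criterion would be fewer, and the documents do not allow that number to be estimated. This review takes no position on which entry rule is right.

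**What to change.** Reconcile the synopsis, Protocol Table 2 footnotes a and c, Protocol 4.1.3, 4.2, 4.4, 7.1, 7.1.1 and 7.1.1.1, and SAP 1.2.3 to one stated OLE entry rule. The rule should say how a prior IP discontinuation bears on entry, by reason, covering each 7.1 criterion and stopping for an immunosuppressant. Record prior IP discontinuation as a flag at Visit 13.

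If the reconciled rule allows any discontinuer to enter:

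- SAP 4.2.11: summarise these participants separately from continuous users.
- SAP 3.5.1: exclude off-drug time beyond the last double-blind dose + 12 weeks from on-treatment adverse event time. This leaves continuous users unchanged, since a last double-blind dose at Week 32 gives 32 + 12 = Week 44, after OLE entry.
- SAP 4.2.4: exclude the off-drug gap from overall exposure.

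The cost is wording changes in both documents, one flag at Visit 13 and slightly more analysis work.

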#### **4.1.4 Study Conduct Mitigation During Study Disruptions Due to Cases of Civil Crisis, Natural Disaster, or Public Health Crisis**

The guidance given below supersedes instructions provided elsewhere in this clinical study protocol (CSP) and should be implemented only during cases of civil crisis, natural disaster, or public health crisis (eg, during quarantines and resulting site closures, regional travel restrictions, and considerations if site personnel or study participants become infected with SARS-CoV-2 or similar pandemic infection) which would prevent the conduct of study-related activities at study sites, thereby compromising the study site staff or the participant's ability to conduct the study. The Investigator or designee should contact the study Sponsor representative to discuss whether the mitigation plans below should be implemented. The study participants will be required to complete the screening and randomization visits on site prior to having the option to participate in the mitigation plans.

To ensure continuity of the clinical study during a civil crisis, natural disaster, or public health crisis, changes may be implemented to ensure the safety of study participants, maintain compliance with Good Clinical Practice (GCP), and minimize risks to study integrity.

Where allowable by local health authorities, ethics committees, healthcare provider guidelines (eg, hospital policies) or local government, these changes may include the following options:

- Obtaining consent for the mitigation procedures (note, in the case of verbal consent, the Informed Consent Form (ICF) should be signed at the participant's next contact with the study site).
- Re-screening: Additional re-screening for screen failure and to confirm eligibility to participate in the clinical study can be performed in previously screened participants. The Investigator should confirm this with the designated study physician.
- Home or Remote visit: Performed by a site qualified Health Care Professional (HCP) or HCP provided by a third-party vendor (TPV).
- Telemedicine visit: Remote contact with the participants using telecommunications technology including phone calls, virtual or video visits, and mobile health devices.
- At-home IP administration: Performed by a site qualified HCP or HCP provided by a TPV, or by the participant or the participant's caregiver, if possible. Additional information related to the visit can be obtained via telemedicine.

- If participant testing is performed due to the public health crisis the results may be documented for this study.

For further details on study conduct during civil crisis, natural disaster, or public health crisis, refer to [Appendix H](#).

## 4.2 Scientific Rationale for Study Design

As detailed in Section 2, the central role of eosinophilia in the pathophysiology of BP suggests that a direct eosinophil-depleting approach, as provided by benralizumab, may prove beneficial in the treatment of BP. There are several lines of evidence that indicate eosinophils are central to the disease pathology of BP ([Amber et al 2018b](#), [Messingham et al 2019](#)).

This is a Phase 3 study designed to evaluate the efficacy and safety of benralizumab in the treatment of participants with BP.

This study's inclusion/exclusion criteria are designed to capture a population appropriate for treatment with benralizumab. For inclusion in the study, participants should be candidates for systemic corticosteroid therapy based on the extent or seriousness of their disease. The study will include participants with classic, predominantly cutaneous BP. Participants with drug-induced BP, a small subset of BP participants; will be excluded as the initial treatment approach in these participants is discontinuation of the offending drug.

The study's randomized, double-blind, placebo-controlled, parallel-group treatment period is designed to demonstrate the efficacy and safety of benralizumab.

The primary endpoint chosen is to assess the effect of benralizumab on sustained disease remission. This endpoint was chosen based on outcome measures recommended by the consensus statement ([Murrell et al 2012](#)) and feedback from a panel of clinical experts on BP who were consulted on the feasibility of using benralizumab as a treatment for BP and on the optimal study design. While OCS are the only well-established treatment for BP and highly effective for achieving disease control, the relapse rate is high on tapering and discontinuation, and OCS are associated with significant morbidity and mortality. The overall treatment goal in participants with BP is to reduce the dose of OCS and associated side effects while maintaining disease control. The ability of participants to taper steroids and achieve complete remission off steroids (the proposed primary variable) and the proportion of participants who have relapsed after tapering steroid therapy (the first key secondary variable) are therefore clinically important outcomes in this participant population. Both are accepted endpoints for BP studies ([Murrell et al 2012](#)). The key secondary variables, proportion of participants who remain relapse-free up to Week 36, cumulative OCS exposure (mg/kg) up to Week 16 and up to Week 36, and change in BPDAI activity and pruritus scores at Week 36, will also provide an opportunity to assess benralizumab's efficacy in participants with symptomatic BP.

The OLE will provide an opportunity to assess long-term safety and tolerability, in addition to assessing efficacy of benralizumab monotherapy, and to ensure that all participants who complete the double-blind treatment period can have access to treatment with benralizumab.

#### 4.3 Justification for Dose

The approved dosing regimen of benralizumab in severe asthma is 30 mg Q4W for the first 3 doses, followed by 30 mg Q8W thereafter. In patients with severe asthma (SIROCCO [Bleecker et al 2016] and CALIMA [FitzGerald et al 2016]), treatment with benralizumab 30 mg Q8W and Q4W resulted in near complete blood eosinophil depletions for both the Q8W and Q4W dosing regimens. Treatment with benralizumab 30 mg Q4W has also been shown to reduce blood and tissue eosinophilia in tissues of patients with varied clinical subtypes of HES where patients have higher blood eosinophils and significant organ manifestations of eosinophilic inflammation (Kuang et al 2019).

Patients with BP have peripheral blood and tissue eosinophilia and elevated eosinophils in tissue (Kridin 2018). Data is available for benralizumab pharmacokinetics (PK) in blood, lung tissue and bone marrow (Laviolette et al 2013), but not in skin. As the skin compartment is thicker than lung tissue and not as vascular skin tissue may follow different PK and may benefit from a higher initial dose. This strategy aligns with other biologics in skin diseases where a higher initial dose is indicated to ensure skin partitioning in an efficient manner. Efficient delivery of drug to diseased tissue is paramount in this disease given the acute and marked symptomatology.

The PK of benralizumab are well-characterized (Wang et al 2017), and benralizumab is expected to demonstrate consistent PK across different disease populations. According to Population PK modeling in asthma patients, a loading dose of 60 mg benralizumab followed by 30 mg benralizumab Q4W SC will result in greater exposure and rapid partitioning into the skin to ensure eosinophil depletion, maximizing the potential of disease control in patients with BP. Post loading dose, the more frequent regimen, 30 mg Q4W, was selected to maintain eosinophil depletion in BP patients, as there is high eosinophil burden in blood and skin.

The safety and tolerability of a range of doses of benralizumab have been demonstrated. In Phase 3 asthma studies, over 3500 patients have received 30 mg doses of benralizumab. In Phase 2 and 3 studies in patients with COPD, over 1100 patients have received benralizumab 30 mg, and over 1100 patients have received benralizumab 100 mg. No dose-limiting safety issues have been identified with dosing in clinical studies up to 100 mg for 52 weeks (refer to the Investigator Brochure for details). In clinical trials in COPD using the 100 mg dose, tolerability was demonstrated in 450 patients aged 65 years to 74 years old and 166 patients aged over 75 years old received benralizumab.

Therefore, the proposed dosing regimen for benralizumab in this study is 60 mg loading followed by 30 mg SC Q4W.

